6.1.2. Vital Signs, Height and Weight

Vital signs will be collected according to the Schedule of Visits and Assessments ([Section 1.3](#)):

Blood pressure, heart rate, and temperature will be measured. Blood pressure will be collected while the subject is sitting/resting for at least 5 minutes.

Height will be collected at Day 1, Week 24 and end of study Week 52/Early Termination.

Subject to void prior to weight being taken and remove any jackets, outerwear and shoes. Remove any objects of significant weight (i.e. cell phones, wallet, key chains). A 5% unintentional weight loss from Baseline should be reported to the medical monitor.

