- **Duration of IGA of 0** = the date of first observation of IGA > 0 - the date of first observation of IGA of 0 and stop treatment. The duration of IGA of 0 for subjects who end treatment in IGA success will be censored at the last disease assessment date. This is for subjects who achieve IGA of 0 and stop the treatment. Subjects who achieve IGA of 0 but never stop treatment will be excluded from the analysis. For subjects who achieve IGA of 0 but stop the treatment later, the duration starts from the date of stop treatment. Only the first IGA of 0 duration will be analyzed.
- **Duration of IGA of 0 or 1** = the date of first observation of IGA > 1-the date of first observation of IGA of 0 or 1 + 1. The duration of IGA of 0 or 1 for subjects who end treatment in IGA of 0 or 1 will be censored at the last disease assessment date. Only the first IGA of 0 or 1 duration will be analyzed.
- **Disease recurrence** = the date of first observation of IGA of 2 or above after achieving IGA of 0 and stop treatment - the date of first observation of IGA of 0 + 1. Only the first disease recurrence will be analyzed.
- **Treatment-free interval** = the date of re-starting study drug due to IGA score above 0 - the date of stop treatment due to attainment of score of IGA of 0 +1, among subjects who achieve a “completely clear” IGA and stop treatment to all lesions. If subjects never re-start study drug after stopping treatment, the treatment-free interval is censored at the end of study date. Only the first treatment-free interval will be analyzed.
- **Weight of IP (g)** = dispensed can weight – returned can weight.
- **BMI (kg/m²)** = (weight in kg)/[(height in cm/100)²]. Day 1 height will be used for BMI derivation upto Week 24. For visits including week 24 through week 36, week 24 height

will be used to derive BMI. Week 52 BMI is derived using the height and weight collected at the same visit. This derivation is applied since height is not collected at all visits.

- **BMI Categories:**

- Underweight: $BMI < 18.5$
- Normal: $18.5 \leq BMI \leq 24.9$
- Overweight: $25.0 \leq BMI \leq 29.9$
- Obese: $BMI \geq 30.0$

- **WI-NRS 4-point reduction** = achievement of a 4-point reduction in WI-NRS pruritus score post-baseline compared to baseline, calculated only for subjects with a pruritus score of ≥ 4 at baseline.
- **Itch-free state** = achievement of in WI-NRS of 0 or 1.

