9.4. Vital Signs

Descriptive summaries of observed values, changes, and percent changes from baseline will be calculated for systolic blood pressure, diastolic blood pressure, heart rate, height, weight, body mass index, and oral body temperature by group and study visit.

Categorical percent changes in weight (i.e., shifts from baseline) by group will be summarized by the number of subjects who gain or lose $\geq 5\%$ of their baseline body weight during the course of the study, as well as subjects who gain or lose $\geq 10\%$ of their baseline body weight over the course of the study by groups and study visit.

BMI is derived as specified in Section [6.1.7](#). Shift tables for subjects who shift from their baseline BMI category (underweight, normal, overweight, obese) to a different BMI category throughout the course of the study will be provided by groups and study visit.

Shift tables for weight and BMI will also be summarized by intentional and unintentional weight loss (defined from question on vital sign eCRF). Vital signs summaries will use primary baseline for Cohort 1 Group 1 and OLE baseline for Cohort 2. Overall group will be summarized using Safety baseline.

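### In adults, SAP 6.1.7 swaps in a newly measured height at Weeks 24 and 52, which adds avoidable, roughly symmetric noise to BMI change and the BMI-category shift table

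*SAP*

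**What the plan says.** Protocol 6.1.2 sets the height schedule: "Height will be collected at Day 1, Week 24 and end of study Week 52/Early Termination". It applies to all subjects. Weight is taken at every clinic visit.

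SAP 6.1.7 defines BMI as weight in kg over squared height in metres and assigns heights to visits in three steps:

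- Before Week 24: "Day 1 height will be used for BMI derivation upto Week 24".
- Weeks 24 and 36: "For visits including week 24 through week 36, week 24 height" is used.
- Week 52: "Week 52 BMI is derived using the height and weight collected at the same visit".

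The reason given is "This derivation is applied since height is not collected at all visits". There is no split by age, although SAP 3.1 admits subjects from 9 years upward. One set of category limits (18.5, 25.0, 30.0) serves everyone.

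SAP 9.4 summarises BMI, its change and its percent change by group and visit. It adds "Shift tables for subjects who shift from their baseline BMI category (underweight, normal, overweight, obese) to a different BMI category", and repeats these tables by intentional and unintentional weight loss. The same section tabulates gain or loss of at least 5% and at least 10% of baseline body weight, which needs no height.

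**The concern.** The stated reason explains why a height must be carried forward to visits without a reading. It does not explain why an adult's height should be replaced. In a growing child the newer height is the better one. In an adult the difference between two readings a few months apart is almost all measurement error, and BMI divides by height squared, so the relative error in BMI is about twice that in height.

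BMI change at Weeks 24, 36 and 52 then mixes weight change with height error, and an adult whose weight has not moved can appear as a category shift. Protocol 3.3.2 names weight loss among the most common adverse events of oral roflumilast, so a reader of a long-term safety report will look at these displays. Apart from the removal of shoes, neither document standardises the height reading, asks for replicates or checks for implausible adult height change.

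**Working it through.** The documents give no height error, BMI distribution or expected shift rate, so there is no planned figure to reproduce. The check has three parts.

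**1. Exact arithmetic at constant weight.** Formula: BMI = weight / (height/100)².

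| Weight | Height used | BMI | Category |
|---|---|---|---|
| 72.0 kg | 170 cm | 24.9 | normal |
| 72.0 kg | 169 cm | 25.2 | overweight |
| 87 kg | 170 cm | 30.1 | obese |
| 87 kg | 171 cm | 29.8 | overweight |

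A 1 cm difference is enough to cross a limit in either direction.

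**2. Size of the false change.** With independent errors of SD s on two readings, the SD of the false BMI change is about BMI × 2 × √2 × s / height. At BMI 28, height 170 cm and s = 1.0 cm this is 28 × 2 × 1.414 × 1.0 / 170 = 0.47 kg/m². A true 5% weight loss at the same BMI is 0.05 × 28 = 1.4 kg/m².

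**3. Simulation of category shifts.** Assumed, not in the documents: adult BMI lognormal with median 27.5 and log SD 0.21; height mean 170 cm, SD 10 cm; independent height errors; 2,000,000 draws; BMI rounded to 0.1. Weight change has mean zero and SD 0%, 3%, 4% or 5%.

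| | Error SD 0.5 cm | 1.0 cm | 1.5 cm |
|---|---|---|---|
| SD of false BMI change (kg/m²) | 0.24 | 0.48 | 0.72 |
| Adults shifting category, weight unchanged | 2.5% | 5.0% | 7.5% |
| Adults in a different category from the fixed-height result, weight SD 3-5% | about 2.5% | about 5% | about 7.5% |
| Rise in total tabulated shifts, weight SD 3-5% (points) | 0.2-0.4 | 0.8-1.3 | 1.8-2.7 |

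The last two rows differ because real weight change already moves many adults. With fixed height, about 9%, 12% and 15% shift at weight SDs of 3%, 4% and 5%. Height error pushes some subjects over a limit and pulls others back, so most of the individual reclassification cancels in the counts. At a weight SD of 4%, downward shifts go from 6.3% to 6.4% (error SD 0.5 cm) or 6.8% (1.0 cm). With weight unchanged, half of the false shifts are downward and half upward.

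Other assumed BMI distributions (mean/SD 26/5, 28/6, 30/7; height SD 9.5 cm) give 2.2-2.7%, 4.4-5.4% and 6.6-8.1% at constant weight, and 1.1-1.3% for an error SD of 0.25 cm. With one fixed height, shifts at constant weight are zero by construction.

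**Which visits are affected.** Weeks 24 and 36 share the Week 24 height, and Week 52 has its own. Weeks 4 and 12 use the Day 1 height. For Cohort 1 Group 1, however, SAP 6.1.1 and 9.4 take vital-sign changes from the primary baseline. For subjects previously on roflumilast this lies in ARQ-154-203, before their first dose there, while their Day 1 data come from the final visit of that study (Protocol 1.3). The SAP does not say which height enters that baseline BMI, so their early visits may mix heights too.

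**The case against.** **The weight signal is read without height.** This stands. The 5% and 10% tables in SAP 9.4 use weight alone. Protocol 7.2.6 asks for weight shift tables, not a BMI one. Reporting to the medical monitor (Protocol 6.1.2) and the weight criterion in Protocol 5.4.3 also rest on percent weight loss. A reader might infer that the derivation hides or mimics drug-related weight loss. The documents do not support that: the noise is symmetric, BMI is not an endpoint, and SAP 6.1.2 plans no inferential analysis.

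**The constant-weight percentages overstate what the tables would show.** This also stands. A reader might turn 2.5%, 5% and 7.5% into about 10, 20 or 30 extra shifts among 400 subjects. Those are upper bounds: they assume that every tabulated subject is an adult with a Week 52 value and that nobody's weight changes. The adult share is not given. The rise in tabulated shifts is the fairer measure of how much less stable late visits would look.

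**A uniform rule using the latest height is defensible, and fixing Day 1 height carries its error into every BMI.** This stands in part. The rule is prespecified and simple. But the Day 1 error is already in every BMI based on Day 1 height, and with one height it nearly cancels in change: a 1 cm error at 170 cm scales the change by about 2 × 1/170 = 1.2%, which is 0.016 of a 1.4 kg/m² change. Simplicity does not justify exchanging an adult's height when an age split costs one line.

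**Conclusion.** The point holds as a minor matter of derivation. In adults the rule adds avoidable noise to BMI change at Weeks 24, 36 and 52 and to the BMI-category shift table, including its split by intentional and unintentional weight loss. It puts about 2.5-7.5% of adults in a different category from the fixed-height result, yet raises total tabulated shifts by only about 0.2-2.7 points. These ranges rest on assumed height-error SDs of 0.5-1.5 cm, an assumed adult BMI distribution, independent errors and a weight-change SD of 3-5%. The direction of net change is not biased, and the body-weight tables are untouched. It is a cheap improvement, not a threat to the safety conclusions.

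**What to change.** In SAP 6.1.7, state that for subjects aged 18 or older at Day 1 the Day 1 height is used for every BMI value. This must cover the baseline as well as all post-baseline visits, including the primary baseline taken from the parent study for Cohort 1 Group 1; otherwise the mismatch only moves to another place. For subjects under 18, keep the re-measured heights as now planned. Height itself stays in the SAP 9.4 summaries, so the later adult readings are still reported.

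The cost is about one sentence in the SAP and one line of code. The downsides are that any Day 1 height error is carried into all adult BMI levels and categories, true height loss in older adults over the year is ignored, and the derivation is split by age.

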APPENDIX 6. CHILDREN'S DEPRESSION INVENTORY 2 (PARENT REPORT)

By [name].					
CDI² PARENT		Child's Name/ID: _____	Child's Sex:  Male  Female Circle One	Date of Birth: _____ / _____ / _____ Year Month Day	
Parent's Name/ID: _____		Relationship to Child: _____	Today's Date: _____ / _____ / _____ Year Month Day		
Child's Age: _____		Child's Grade: _____			
Instructions: For each of the statements below, select one response that best describes your observations of your child in the past two weeks. Indicate your response for each item by circling the number that best corresponds to your choice. You may change an item response by drawing an X through your original choice and selecting a new response. Remember, for each statement, pick one answer that best describes your observations of your child in the PAST TWO WEEKS					
My child		Not at all	Some of the time	Often	Much or most of the time
1. looks sad.		0	1	2	3
2. has fun.		0	1	2	3
3. does not like himself or herself.		0	1	2	3
4. blames himself or herself for things.		0	1	2	3
5. cries or looks tearful.		0	1	2	3
6. is cranky or irritable.		0	1	2	3
7. enjoys being with people.		0	1	2	3
8. thinks that he or she is ugly.		0	1	2	3
9. has to push himself / herself to do schoolwork.		0	1	2	3
10. has trouble sleeping at night.		0	1	2	3
11. looks tired or fatigued.		0	1	2	3
12. seems lonely.		0	1	2	3
13. enjoys school.		0	1	2	3
14. spends time with friends.		0	1	2	3
15. is showing worse school performance than before.		0	1	2	3
16. does what he or she is told.		0	1	2	3
17. has disagreements and conflicts with others.		0	1	2	3

MHS Copyright © 2011 [name] and Multi-Health Systems Inc. All rights reserved.
In the United States, [name], [name]. In Canada, [name], [name], [name], [contact]. Internationally, [contact], Fax, [contact] or [contact].

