- **PHQ-8** = sum of the 8 questions (individual questions scored as Not at all=0, Several days=1, More than half the days=2, and Nearly every day=3; range for score 0 to 24). If more than 1 item is missing the score should not be calculated. If 1 item is missing the score is calculated as (sum of answered items*8)/number of answered items.
- **PHQ-A** = sum of the 8 questions (individual questions scored as Not at all=0, Several days=1, More than half the days=2, and Nearly every day=3, (range for score 0 to 24). If more than 1 item is missing, the score should not be calculated. If 1 item is missing, the score is calculated as (sum of answered items*8)/number of answered items.
- **CDI-2** = total score is calculated as a sum of the 17 questions (individual questions scored as much or most of the time=3, often=2, some of the time=1, Not at all=0; range for score 0 to 51).
 - CDI-2 emotional problem scale is a sum of 9 questions (Q1, Q3-6, Q8, Q10 -12)
 - CDI-2 function problem scale is a sum of 8 questions (Q2, Q7, Q9, Q13-17)
- **Scalpdex score transformation** = Scalpdex is rated on a 1 to 5 scale which will be transformed to 0 to 100 Scale where 1=0; 2=25; 3=50; 4=75; 5=100. This transformed score is used to calculate scale scores.
- **Scalpdex Emotions Scale** = average of (Q2, Q4, Q5, Q6, Q7, Q9, Q10, Q11, Q12, Q14, Q16, Q17, Q19, Q20, Q22) after transforming to 0 to 100 scale as mentioned above.

Q refers to question number. Q19 will be reverse scored i.e., 1=100; 2=75; 3=50; 4=25; 5=0.

- **Scalpdex Symptoms Scale** = average of (Q1, Q3, Q8) after transforming to 0 to 100 scale as mentioned above. Q refers to question number.
- **Scalpdex Functioning Scale** = average of (Q13, Q15, Q18, Q21, Q23) after transforming to 0 to 100 scale as mentioned above. Q refers to question number.
- **Scalpdex Total Score** = calculated as mean of all the 23 scalpdex questions using the transformed scale of 0 to 100. Q19 will be reverse scored i.e., 1=100; 2=75; 3=50; 4=25; 5=0 while calculating the mean. Q refers to question number.
- **Total % BSA (body surface area)** = sum of coverage areas of head, limbs, upper limbs, and lower limbs.
- **Change from baseline** = value at current time point – value at baseline. This is derived separately for primary baseline and OLE baseline.
- **Percent change from baseline** = (value at current time point – value at baseline)/value at baseline. This is derived separately for primary baseline and OLE baseline.

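### SAP 6.1.7 adds the 17 CDI-2 parent items without reversing the five favourably worded ones, so the total and functional scores are mis-keyed as written

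*SAP*

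**What the plan says.** SAP 6.1.7 (Derived Variables) gives one code map for every CDI-2 item. The "total score is calculated as a sum of the 17 questions (individual questions scored as much or most of the time=3", with the lower responses coded 2, 1 and 0 and a stated range of 0 to 51. The two subscales are also plain sums. For emotional symptoms the rule reads "CDI-2 emotional problem scale is a sum of 9 questions (Q1, Q3-6, Q8, Q10 -12"), and none of those nine items is favourably worded. For functioning, where all the favourable items fall, it reads "CDI-2 function problem scale is a sum of 8 questions (Q2, Q7, Q9, Q13-17").

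Neither SAP 6.1.7 nor SAP 9.6 (CDI-2) reverses any CDI-2 item or says that stored values are already keyed. In the same section, the Scalpdex rule does state a reversal: "Q19 will be reverse scored".

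Protocol Appendix 6 prints the codes 0, 1, 2, 3 in the same order for all 17 items. Five of them are favourable:

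- Q2: the child has fun
- Q7: "enjoys being with people"
- Q13: "enjoys school"
- Q14: "spends time with friends"
- Q16: "does what he or she is told"

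Protocol 6.1.6 and 6.8 treat a higher CDI-2 raw score as worse. SAP 9.6 plans observed values, changes and percent changes for the total and both scales, by group and visit.

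**The concern.** A child whose parent reports frequent fun and frequent time with friends gains problem points under the SAP rule. That contradicts the name of the scale and the direction in which the protocol reads the score. The Scalpdex rule shows that this SAP writes out a reversal where one is intended, so silence on CDI-2 cannot safely be read as an implied one.

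CDI-2 is the only depression instrument for ages 9 to 11, because PHQ-A and C-SSRS start at 12. A functional score that can move the wrong way would misdescribe the psychiatric safety of the youngest children, for a drug class in which psychiatric events are a known concern with oral use (Protocol 3.3.2).

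**Working it through.** **The plan's own figure.** 17 items × 3 = 51, which matches the stated range. The emotional list (9 items) and the functional list (8 items) together cover Q1 to Q17 with no gap or overlap. The range is 0 to 51 with or without reversal, so it does not test the keying.

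**Where the favourable items sit.** All five are in the functional scale; its other three items (Q9, Q15, Q17) are problem items. None is in the emotional scale, so that scale has no error.

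**Size of the error in an observed score.** Let N be the sum of the problem items (12 in the total, 3 in the functional scale) and P the sum of the five favourable items after reversal (3 minus the code), so P runs from 0 to 15. The unreversed sum of the five is 15 − P.

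- SAP score = N + 15 − P
- Keyed score = N + P
- Error = SAP − keyed = 15 − 2P

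The error runs from +15 (P = 0) to −15 (P = 15). It is always odd, so it is never zero. The five items have 4^5 = 1,024 response patterns. The error is at least 5 points when P ≤ 5 or P ≥ 10. The pattern counts for P = 0 to 5 are 1, 5, 15, 35, 65 and 101 (sum 222), and by symmetry P = 10 to 15 gives another 222, so 444 patterns in all. This counts patterns and is not a prevalence among children.

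**Direction.** Give every item the same severity s, from 0 (best) to 3 (worst). The SAP functional score is 3s + 5(3 − s) = 15 − 2s and the keyed one is 8s. The SAP total is 12s + 5(3 − s) = 15 + 7s and the keyed one is 17s.

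| Severity s | Functional, SAP | Functional, keyed | Total, SAP | Total, keyed |
|---|---|---|---|---|
| 0 | 15 | 0 | 15 | 0 |
| 1 | 13 | 8 | 22 | 17 |
| 2 | 11 | 16 | 29 | 34 |
| 3 | 9 | 24 | 36 | 51 |

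On this path the functional scale runs backwards and the total is compressed.

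**Ends of the range.** The lowest response to all 17 items gives SAP 0, keyed 15. The highest response to all gives SAP 51, keyed 36. The ends therefore do not mean best and worst.

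**Loss of meaning at one value.** A SAP score of 15 requires N = P, so the keyed score is 2P. For the total that allows every even value from 0 to 30. For the functional scale N is at most 9, so it allows every even value from 0 to 18.

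**Change from baseline.** The constant 15 cancels. SAP change = ΔN − ΔP and keyed change = ΔN + ΔP, so the error is −2ΔP. It is zero only if the favourable-item sum has not changed. If every item worsens by one grade, the functional score changes by 3 − 5 = −2 (keyed +8) and the total by 12 − 5 = +7 (keyed +17).

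**The case against.** **The stored values are unknown.** The instrument's scoring key and the eCRF coding are not in the documents, and Protocol 6.1.6 calls Appendix 6 an example of the form. If the database holds keyed values, the output would be correct. This stands as a limit on what can be said about delivered results. It does not rescue the text: the SAP ties the codes to response words for every item, and if the values are keyed, that map is wrong for five of them.

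**The reach may be close to nil.** Much of this stands.

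- The design text sets a minimum age of 12 for Cohort 2, although the numbered criteria admit age 9 and above for all subjects.
- Cohort 1 Group 2 (about 10 subjects) is listings only, and the documents do not say whether those listings show derived scores or item responses.
- That leaves Cohort 1 Group 1. SAP 9.5 and 9.6 say that neither PHQ-A nor CDI-2 was assessed in its parent study, ARQ-154-203, which suggests few or no minors there; its age range is not given.
- Cohort 1 Day 1 data are carried over from the parent study (SAP 6.1.1), so a Group 1 child may have no CDI-2 baseline and the change tables may hold few or no subjects.

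Against this, observed values at Weeks 4, 12, 24, 36 and 52 need no baseline, and SAP 6.1.6 still plans an age group of 9 to 11.

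**The profiles are constructed.** The uniform-severity, all-lowest and all-highest cases illustrate the error and do not forecast it. The identity 15 − 2P does not depend on them.

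**No decision hangs on it.** CDI-2 is descriptive, feeds no primary endpoint, and no SAP output applies a cut-off. This also stands.

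**Conclusion.** The SAP rule is wrong as written. On the printed codes, every observed total and functional score from a complete form is off by 15 − 2P, between +15 and −15 points and never zero. Change scores are off by −2ΔP. The emotional scale is correct.

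That the SAP states no reversal, and that its code map is wrong for five items, rests on the text and is firm. That delivered scores would be wrong assumes that the database stores the printed response codes, which the documents do not settle. Severity is minor, because the scores are descriptive and few or no children aged 9 to 11 may appear in a table.

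**What to change.** First, confirm from the instrument's scoring key and the eCRF how the item values are stored.

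- If they are the printed response codes, add to SAP 6.1.7 that Q2, Q7, Q13, Q14 and Q16 are scored as 3 minus the response before the total and functional scores are computed.
- If they are already keyed, say so, correct the code map for those five items, and do not reverse again.

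The raw score referred to in Protocol 6.1.6 and 6.8 is not defined item by item. It should be reconciled with the SAP total so that both are keyed the same way. No threshold or clinical rule needs to change for this.

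The cost is one check, one SAP sentence and at most a one-line recode. No new data are needed, because the scores can be re-derived from stored item responses.
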